1.3 Method Of financing of the investigation clinic

The study is financed by the sponsor. A contract/agreement will be stipulated between the sponsor and the experimental site where compensation and responsibilities are established. A draft of this convention was submitted to approval of the competent Ethics Committee.

1.4 Device Doctor

Nova.Emostop Re-epithelizing [Acid hyaluronic linear 0.2%]

The device Yes presents in formulation gel to basic Of acid hyaluronic linear. Yes deals with Of a device medical based substances, non-sterile. The formulation does not contain substances of animal origin, substances deriving from human blood or tissues, CRM substances or substances with pharmacological action ancillary. This medical device falls into class IIb, based on the classification criteria expressed in the EU Regulation on medical devices 2017/745, Annex VIII, paragraph 5.4, rule 4 That defines "Everyone the devices Not invasive in contact with there skin or there mucosa injured they fall... in the class IIb if they are intended to be used primarily for skin wounds that have vulnereated The dermis or there mucosa And That can heal Alone second intention,".

Intended use : The medical device promotes the healing of wounds thanks to its action Hyaluronic acid moisturizer. Hyaluronic acid deposited on the wound surface forms a film moisturizing That protects The tissue give it agents external And maintains The correct degree Of hydration promoting there healing from the wound.

Directions : treatment Of injuries acute superficial, burns superficial And small wounds.

Documento Studio WOUND-H Valutazione prestazioni e sicurezza [acido ialuronico lineare per il trattamento delle ferite]	Codice NA-01-23		
v. 2 del 26 giugno, 2023			

Traceability: there traceability of the device And guaranteed from the a number identifier of the lot Of production.

Materials That they enter in contact with The body human: Everyone the materials That make up The device they have a long history Of usage within clinical e a proven one profile of safety.

They are:

High molecular weight sodium hyaluronate (2500-3500

Kd)D-Panthenol

Triethanolamine

(TEA)Carbomer 940

Symdiol 68T

Medical or surgical procedures related to the use of the device and experience necessary for its use usage

The device must be applied to the wound which must then be covered with an appropriate bandage. Considered there simplicity from the procedure Of application That Not differs from numerous others devices having the same indications, the device can be applied by healthcare personnel (doctors or nurses) without there need Of a specific training.

2 Introduction And rational:

Wound healing is a complex and dynamic process, which is still far from being completely understood. Wounds can be classified based on different characteristics such as trigger factor, exposure to the external environment, the depth of the wound, the period of time recovery, the potential risk of infections ¹. Two main processes are involved in healing of wounds: regeneration and repair. Regeneration involves the activation of stem cells in able to reconstitute the integrity of the tissue which will be indistinguishable from the tissue before the injury. To the Conversely, repair involves the formation of fibrotic scar tissue in which the architecture and the functionality of the original tissue are partially lost. Wound healing can be classified into three different categories: by primary, secondary or tertiary intention. The healing of wound For intention primary happens when there is a minimal loss Of tissue, to example suture from the wounded or taped. This wound will heal with a thin, clean scar, low inflammation, edema and ache. Wound healing by secondary intention occurs when part of the tissue is lost And there is a defect Very more great. In This case, The process restorative And Very more complicated That involves a greater inflammation, edema And ache prolonged For a time more long respect at the

Documento Studio WOUND-H Valutazione prestazioni e sicurezza [acido ialuronico lineare per il trattamento delle ferite]	Codice NA-01-23	v. 2 del 26 giugno, 2023	
--	---------------------------	--------------------------	---

wound healing with primary intention. Wound healing by tertiary intention yes verify when a process For intention secondary he comes intentionally interrupted And there wound will be closed mechanically, for example After That Yes And format the fabric of granulation.

Many strategies And products I am States proposed to the end Of improve there healing from the wounds, reduce The pain and morbidity for patients such as wound dressings, growth factors, substitutes for skin, there dressing of the collagen, insulin topical, the antioxidant, there room hyperbaric, etc.¹ The acid hyaluronic (HAS) And state discovery In the 1934 from Meyer And Palmer In the vitreous bovine eye. AND aglycosaminoglycan present in nature That, in virtue from the her viscosity, elasticity And other property rheological, acts as lubricant eye And as fluid lubricant And shock-absorbing injoints. He comes product come on fibroblasts inside of from the membrane mobile phone And Therefore released in space extracellular. Inside of from the skin, carries out a role important in hydration of the space extracellular; constitutes a matrix For hold up the normal functions from the cells; has Also functions In the filling of the space, in the lubrication, in the healing from the wounds, in the modulation from the cells inflammatory And in scavenging of the radicals free^{2,3}. There concentration Of HAS in the epidermis And Of 15 µg/g And In the dermis And Of 740 µg/g; there mass molecular Of HAS in the skin And Of 1 kDa. IT HAS native And a chain polysaccharide linear similar to the HA In the dermis. AND a gel viscoelastic translucent That can be obtained in highly purified form from rooster combs or through bacterial fermentation. Not has specificity Of species And The risk Of a reaction Of hypersensitivity And Like this Bass That Not And necessary The test cutaneous. There her mass molecular varies Between 0.1 And 2.5 kDa. A gram Of HAS can bind until to 6 litres Of waterfall. That is it means That greater And there percentage Of HAS in a product, greater will be there her capacity Of hold back the water. Thank you to the his remarkable potential biomedical And Of regeneration of the fabrics, It has And widely employee In the treatment from the wounds under different formulations as gauze, creams And gel⁴, showing results clinical significance⁵⁻¹¹.

3 Risks And benefits clinicians of the device

AND was prepared a careful one procedure Of check of the risks connected with use of the device. The level Of Everything is fine risk And state valued in basic at the her severity and at the chance That it Yes check. The level of risk of all risks residues And acceptable result.

The clinical benefits of the device are supported by substantial supporting scientific literature the use of hyaluronic acid-based devices to improve wound regeneration. For an analysis more detailed from the literature relevant see there Investigator Brochures.

4 Goals:

The primary objective of the study is to evaluate the safety and performance of a medical device Of Class IIB to basic Of acid hyaluronic lineare used In the treatment from the wounds post-surgery. The outcomes of the study are the improvement of wound healing assessed through the Clinical Healing

Documento Studio WOUND-H Valutazione prestazioni e sicurezza [acido ialuronico lineare per il trattamento delle ferite]	Codice NA-01-23	
v. 2 del 26 giugno, 2023		

score (score from 0 to 5), That includes there assessment Of: redness, edema,

Documento Studio WOUND-H Valutazione prestazioni e sicurezza [acido ialuronico lineare per il trattamento delle ferite]	Codice NA-01-23		
v. 2 del 26 giugno, 2023			

suppuration, healthy granulation tissue and signs of re-epithelization; the percentage of patients with wounds completely healed at day 30 post-treatment; the pain perceived by the patient when changing from the dressing; there frequency of events adverse.

Team Of operators involved in study

The team Of operators involved in study And Like this composed:

Scientific director and coordinator of the study: [name]

Members effective of the team: [name]

All members of the team are surgeons specializing in Physiatry belonging to the Operating Unit Simple Rehabilitation Nursing Home Villa Sofia. The CVs of the team members are available in attached hereto clinical protocol.

5 Drawing Of the Study

This is an interventional, single-center study. The aim of the study is to evaluate the safety and performance of a class IIB medical device based on linear hyaluronic acid in treatment from the wounds surgical.

Patients who have undergone surgery for knee prosthesis implantation will be chosen hip and recruited based on the selection criteria described below. Patients will be randomized into two groups in which the control group will receive the normal standard therapies for the treatment of wound (typically cleaning and disinfection only) while the treated group will receive two applications daily use of the medical device. The following visits are scheduled for patients: screening (visit 0) to collect the patient's demographic and clinical data, compliance with the inclusion/exclusion criteria; Baseline (visit 1) evaluation of the wound through the Clinical Healing score and start of treatment; follow up 1 (visit 2 – 7 days of treatment) clinical evaluation of the wound, Clinical Healing score, pain assessment upon dressing change; follow up 2 (visit 3 – de-suturing of the wound (18-20 days Of treatment) assessment clinic, Clinical Healing scores, assessment ache to the exchange dressing; follow up 3 (visit 4 – 30 days of treatment) clinical evaluation, Clinical Healing scores, assessment ache to the exchange dressing, determination healing wound (self completely cured or not). A photographic documentation of the wound during the healing process will come collected at visits 1, 2, 3 and 4. For safety assessment all adverse events and events adverse serious they will come sign in And evaluated in relation to those to report from the literature scientific Fordevices similar doctors.

Documento Studio WOUND-H Valutazione prestazioni e sicurezza [acido ialuronico lineare per il trattamento delle ferite]	Codice NA-01-23		 NOVA ARGENTIA
v. 2 del 26 giugno, 2023			

Scheme of the Clinical Healing Score ¹²

Healing score	Wound characteristics
5 – excellent	All wound area is pink; no bleeding on palpation; no granulation tissue; no connective tissue at incision margin.
4 – very good	Less than one quarter of wound area is red, no bleeding on palpation, no granulation tissue; no connective tissue at incision margin.
3 – good	Less than half of the wound area is red; no bleeding on palpation; no granulation tissue; no connective tissue at incision margin.
2 – poor	More than half of the wound area is red; bleeding on palpation; granulation tissue evident; incision margin not epithelialised.
1 – very poor	Two or more of the following features: More than half of the wound area is red; bleeding on palpation; granulation tissue evident; no epithelium at incision margin; infection present with suppuration.

5.1 Scheme of the protocol clinical

Visit 0 Screening: collection information clinics on the patient, inclusion

Visit 1 Baselines: assessment clinic, Clinical Healing scores, photography from the wound, start Treatment.

Visit 2 Follow up 1 (7 days Of treatment): assessment clinic, Clinical Healing scores, assessment a che to the dressing change, assessment reactions adverse, photography from the wound.

Visit 3 Follow up 2 (at the desaturation): assessment clinic, Clinical Healing scores, assessment a che to the dressing change, assessment reactions adverse, photography from the wound.

Visit 4 (30 days Of treatment): assessment clinic, Clinical Healing scores, assessment a che to the exchange dressing, determination healing wound, photography from the wound And collection events adverse.

5.2 Population in study

The study concerns the population of adult patients who have undergone surgery knee, at the hip or to the femur And That present wounds surgical from deal with. The study it will come conducted in a hospital setting at the Simple Operational Unit of Orthopedic Rehabilitation - of the Casa di Villa Sofia rehabilitation care. The enrollment procedure involves screening of patients who are present the UOS Of Rehabilitation orthopaedic Of Villa Sofia with wounds post-surgical And The following enlistment Of those patients respondents to the criteria of the study. Not And expected inclusion Of subjects fragile in study. The patient can retreat give it study in any moment declaring it to the Responsible of the study, in such case he comes asked to the patient Of make the themselves procedures expected for visit 4. The patient is excluded from the study if: 1- deviations from the protocol are detected;2- events arise serious adverse events That prejudice the continuation of study.

Documento Studio WOUND-H Valutazione prestazioni e sicurezza [acido ialuronico lineare per il trattamento delle ferite]	Codice NA-01-23		
v. 2 del 26 giugno, 2023			

5.3 Criteria Of selection of the patients:

- Patients adults with wounds postsurgical.
- Subjects in degree Of respect the procedures of the protocol;
- Signature of the Consent informed

5.4 Criteria Of exclusion:

- pregnancy or feeding time;
- procedures contraceptives inadequate in women fertile;
- treatment concomitant chronic with antiseptics locals, use Of drugs anti-inflammatories (steroids AndNot steroids), analgesics, antineoplastics or immunosuppressants
- use Not therapeutic Of substances psychoactive, abuse Of drugs and/or alcohol
- immunodeficiencies (included infection from HIV)
- Patients oncology;
- allergies Note, hypersensitivity or intolerance to a any from the substances administered in This study
- any condition medical or Not medical That can reduce significantly there possibility Of obtain reliable data e reach the objectives of study
- Participation to Education clinicians with devices or drugs in the 3 months precedents at the visit Of screening.

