10.1 Criteria For The withdraw of the subjects give it study

THE subjects can to interrupt prematurely the investigation clinic in any moment. The interruption premature study is to be understood when the subject has not been subjected to evaluation safety it's at all the clinical evaluations during the investigation clinic.

THE subjects they must to be retreat in following circumstances:

- on own request
- self the investigator believes That Not would be In the improve interest of the subject to continue
- self The subject viola the conditions established In the module Of consent / form information or ignore theinstructions receipts.
- self arise events adverse serious such from to compromise there assessment clinic.

In everyone the cases, The reason For which the subjects they come retreat needs to to be registered in detail in the CRF And in the subject's medical records. If the clinical investigation is terminated prematurely, all of the material of the investigation clinic (CRF complete, partially completed And empty) will be preserved.

Documento Studio WOUND-H Valutazione prestazioni e sicurezza [acido ialuronico lineare per il trattamento delle ferite]	Codice NA-01-23		
v. 2 del 26 giugno, 2023			

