10.3 Politics Of replacement of the subjects retreat

THE subjects That Yes they withdraw give it study Before from the execution from the procedure surgical or immediately after, i.e. before visit 2 (7 days after treatment) they may be replaced by new subjects who meet the inclusion/exclusion criteria. Those who withdraw give it study after visit 2 will be included in the analysis.

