registration of the main efficacy, safety and tolerability endpoints. To be compliant with ISO 14155 standard requires at least 3 monitoring visits. A study start visit, a visit routine and a final visit after the last patient has finished the study. For the present study 8 monitoring visits are planned: an initial visit (centre opening), 6 routine visits and one final visit. Routine visits will be conducted once a month. 100% of the source data will be monitored by the monitor (which means 100% of Source Data Verification). Monitoring will come conducted according to SOPs and will provide an ISO 14155 compliant monitoring report afterwards each visit for the sponsor and investigator. Depending on the quality of the data, they may be necessary more visits Of monitoring a discretion of the sponsor.

12 Changes of the floor Of investigation clinic

The proposed changes to the clinical investigation plan be submitted to the Competent Authority (CA) and to Ethics Committee (EC) of reference. Substantial changes can only be implemented after Obtained the approval of AC/CE. The changes intended to eliminate an apparent immediate danger for subjects can be implemented before receiving AC/EC approval. However, in this case, approval must be obtained as soon as possible after implementation. It is forbidden to apply exceptions to this clinical investigation plan without prior authorization from the AC/EC. The deviations from the clinical investigation plan occurring for any reason must be reported immediately to the Responsible Scientific who will be able to to determine self to exclude The patient from the study.

13 Responsibility relative to the device

The device will be sent to the Villa Sofia Rehabilitation Care Home Pharmacy which will take care of check the good state of conservation of the device and store it in the conditions indicated by manufacturer. THE devices they will come delivered to the Responsible Scientific or his delegate That will provide to store them in the conditions indicated by the manufacturer. The Scientific Manager is responsible for storage and maintenance of devices. Access to the devices is permitted only to members of the team Of research And The withdraw Of Everything is fine device needs to to be annotated on the Device Log File reporting The first name of the member of the team, there date And The lot. THE devices expired or unused they will come retreat give it Sponsors.

14 Calculation from the dimension sample collection

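### With no analysis set stated, randomised patients who deviate, or who withdraw before visit 2, can be left out or replaced by decisions made after randomisation

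*Combined protocol and SAP*

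**What the plan says.** Five sections of the combined protocol and SAP bear on who is analysed.

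- **Section 5.2 (study population)** sets the ground for exclusion: "The patient is excluded from the study if: 1- deviations from the protocol are detected". It gives no threshold for the severity of a deviation and does not say what happens to data already collected.
- **Section 12 (changes to the investigation plan)** says that deviations "must be reported immediately to the Responsible Scientific who will be able to to determine self to exclude The patient from the study". It gives no criteria for the decision.
- **Section 10.1 (withdrawal criteria)** lists among the grounds for mandatory withdrawal: "self The subject viola the conditions established In the module Of consent / form information or ignore theinstructions receipts". The investigator's judgement of the patient's interest is another ground.
- **Section 10.3 (replacement)** says of patients who withdraw "before visit 2 (7 days after treatment) they may be replaced by new subjects who meet the inclusion/exclusion criteria". For the others it says: "Those who withdraw give it study after visit 2 will be included in the analysis".
- **Section 15 (statistical analysis)** gives the tests and the 0.05 level. It names no analysis set and no method for missing values.

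Section 10.2 lets a withdrawn patient ask that nothing further be recorded, so a visit 3 or visit 4 value can be missing. Section 5.6 lists two primary endpoints: the improvement in Clinical Healing score at visit 3 and the reduction in wound size at visit 4.

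**The concern.** Randomisation makes the arms comparable only if the patients compared are those who were randomised. Here two groups have no stated place in the analysis: patients excluded for a deviation, and patients who withdraw before visit 2 and may be replaced. Their place is decided after randomisation, without written criteria for deviations. Sections 5, 5.5 and 5.7 describe no masking, and control patients receive only cleaning and disinfection, so whoever decides can know the arm.

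For patients who withdraw after visit 2, inclusion is stated. What is open for them is how a missing score enters a Mann-Whitney test.

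At stake is the primary comparison. Losing poor healers from the device arm favours the device; losing them from the control arm works against it. Apart from bias, two competent analysts following this plan could analyse different patients.

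**Working it through.** **1. Who is in the analysis, by situation**

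| Situation after randomisation | What the plan says | What is left open |
|---|---|---|
| Deviates | Excluded from the study (5.2); scientific lead decides (12) | Whether the data are analysed; the criteria |
| Ignores instructions | Must be withdrawn (10.1) | Whether 5.2 or 10.3 then governs |
| Withdraws before visit 2 | May be replaced (10.3) | Whether the replaced patient is analysed |
| Withdraws after visit 2 | Included (10.3) | How a missing value is handled |

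Section 15 settles none of the entries in the last column.

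**2. The plan's own figures.** Section 14 gives 53 per group and 5% dropout: 53/0.95 = 55.8, so 56 per arm and 112 in total, as stated. Three patients per arm is about 5% of 56 (2.8). Six is about 5% of the whole trial (0.05 × 112 = 5.6). The 5% is a dropout allowance. The documents give no rate for deviations or exclusions, so these counts are reference points and not limits.

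**3. Illustration.** Assumptions not in the documents: 56 per arm, normal outcome, two-sided Mann-Whitney test at 0.05, the k patients with the poorest early course removed and replaced, and correlation ρ between early course and outcome. There were 40,000 simulated trials per cell, with a Monte Carlo error of about 0.1 percentage point for type I error. Results with no true effect, for ρ = 0 / 0.3 / 0.6:

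| Removed, device:control | Type I error, % | Bias, SD | Falsely finds device better, % (nominal 2.5) |
|---|---|---|---|
| 3:0 | 4.9 / 5.3 / 6.1 | 0 / 0.03 / 0.06 | 2.4 / 3.7 / 5.0 |
| 0:3 | 5.2 / 5.3 / 6.3 | 0 / -0.03 / -0.06 | 2.6 / 1.6 / 1.2 |
| 6:0 | 4.9 / 6.0 / 8.8 | 0 / 0.05 / 0.11 | 2.4 / 4.7 / 8.1 |
| 3:3 | 4.9 / 5.2 / 5.5 | none | – |

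With a true effect of 0.5 SD, power is 72% with no removals, 72 / 78 / 82% with 3:0, and 73 / 67 / 62% with 0:3.

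**4. Check of the bias by hand.** If k patients are removed and replaced, bias ≈ ρ × k × m / 56, where m is the average depth (in SD) of the k lowest of 56. A separate simulation removed the k worst outcomes from one arm without replacement. It gave a shift of 0.112 SD for k = 3 and 0.200 SD for k = 6.

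- k = 3: k × m = 0.112 × 53 = 5.94, and 5.94/56 = 0.106. Times 0.3 and 0.6 this is 0.032 and 0.064.
- k = 6: k × m = 0.200 × 50 = 10.0, and 10.0/56 = 0.179. Times 0.3 and 0.6 this is 0.054 and 0.107.

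Both agree with the table.

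**5. More exclusions or a stronger link.** In that separate simulation (10,000 trials per cell, device-arm exclusions only, no replacement), suppose the excluded patients would have scored 1 SD worse. The bias is then k/56: 3/56 = 0.054, 6/56 = 0.107 and 11/56 = 0.196 SD. Two-sided type I error is 5.6%, 7.2% and 13.3% at 5%, 10% and 20% excluded. If the very worst scores are excluded, it is 8.4%, 16.8% and 40.0%.

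**6. Under the proposed rule.** If every randomised patient is kept with the outcome and replacements are added, type I error is 4.8 to 5.2% in every pattern, and the bias is at most 0.003 SD.

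**The case against.** The strongest reply is that the sections fit together. Section 5.2 gives the ground and section 12 says who decides. Section 10.1 treats ignored instructions as withdrawal, and section 10.3 then keeps the data of anyone who leaves after visit 2. On that reading, exclusion means the end of participation and not the deletion of data. The text is also a rough translation, so one word should not carry much weight. This stands in part. A reader might infer that 5.2 and 10.3 contradict each other, or that 5.2 orders deviators' data to be dropped. The documents support neither: they leave the matter open. Nor does 10.3 say that early withdrawals are left out of the analysis; it only fails to say that they are kept. But the benign reading is itself unstated, it leaves exclusion to unguided discretion, and it does not reach patients lost before visit 2.

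A second reply is that conduct is well controlled: "100% of the source data will be monitored by the monitor" (section 11), and deviations are reported at once (section 12). That makes removals traceable, but does not say who is analysed. Likewise, the morphometric measurement in section 5.7 guards against biased assessment of the wound, not against selective removal of patients.

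A third reply is that the effect is small. With three removals from one arm it is: at most 0.06 SD in the illustration, against a planned effect of 0.5. But nothing ties exclusions for deviation to the 5% dropout allowance.

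**Conclusion.** The omission is certain from the text and should be fixed; the size of its consequence is not known. It concerns deviators and withdrawals before visit 2, whose analysis status is unstated, and the missing values of later withdrawals, whose inclusion is stated.

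Under the illustrative assumptions, with correlation 0.3 to 0.6, three removals from one arm give a type I error of about 5 to 6% and a bias of 0.03 to 0.06 SD. Six give about 6 to 9% and 0.05 to 0.11 SD. A reader might take the six-patient case as an upper limit, or the small three-patient effect as the expected one. Neither follows from the documents, and stronger links or more exclusions give more. A reader might also infer that the result is tilted towards the device. That is not supported either: the direction depends on which arm loses its poor healers, and there is no bias if removals are balanced or unrelated to healing.

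**What to change.** - **Section 15:** state that the primary analysis of both primary endpoints (Clinical Healing score at visit 3, wound-size reduction at visit 4) includes every randomised patient in the assigned arm, regardless of deviation, exclusion, withdrawal or replacement. Prespecify one handling of missing values.
- **Section 10.3:** state that a replacement is an additional patient and that the original patient stays in the primary analysis.
- **Deviations:** use them only to define a per-protocol sensitivity analysis, with patients classified before any data are compared by arm.
- **Sections 5.2, 10.1, 10.3 and 12:** reconcile them so that none acts as a rule for removing data from the analysis. Collect the scheduled endpoint visits after exclusion where the patient's consent allows.

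The cost is wording. The 53 per group and the 112 do not change, and no more patients are recruited than the present replacement rule allows. A few missing values must be handled, and the effect estimate may be slightly diluted. The protection is full only where the outcome is collected. If it is never collected and baseline does not predict it, bias remains: three losses from the device arm alone still give about 0.03 to 0.065 SD at correlations of 0.3 to 0.6.
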